RESEARCH PROTOCOL

TITLE

**Effects of vitamin D₃ supplementation on lung functions and
exercise tolerance in D₃ deficient Asthma COPD Overlap
(ACO) patients**

Date:06/09/2018

Project Summary

Background: Asthma COPD Overlap (ACO) has been described as a distinct disease now-a-days. Several studies have shown positive relationship between serum concentration of 25 hydroxyvitamin D, lung function and exercise tolerance in different group of patients. However, vitamin D supplementation showed significant improvement in lung function status and exercise tolerance in both asthma and COPD patients but no study was found in ACO patients. **Objectives:** To evaluate the effects of vitamin D₃ supplementation on lung function status and exercise tolerance in D₃ deficient, stable patients with ACO. **Methods:** This double blinded placebo controlled trial will be conducted by Department of Physiology Bangabandhu Sheikh Mujib Medical University (BSMMU), Shahbag, Dhaka from March 2018 to February 2019. For this study a total number 70 vitamin D₃ deficient (serum 25 hydroxycholecalceferol <30 ng/ml) male, stable (diagnosed patient, who was not experienced any acute exacerbation, hospitalization, urgent care visits or changes in routine medication within 4 weeks prior to study) patients with ACO of age 40-70 years will be selected. They will be selected from the Out Patient Department (OPD) of the National Institute of Diseases of Chest and Hospital (NIDCH) and will be randomly grouped as A (control) and B (study). All the participants will be matched in terms of age, duration of ACO, duration of smoking, body mass index (BMI), mid upper arm circumference (MUAC), waist hip ratio, occupational status, socioeconomic status, serum

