advised to continue ad lib (according to their own choice) diet. At the very 1st day of the study, the spirometric lung functions will be assessed by measuring forced vital capacity (FVC), forced expiratory volume in 1st second (FEV₁), forced expiratory ratio (FEV₁/FVC%), peak expiratory flow rate (PEFR) and forced mid expiratory flow of FVC (FEF_{25-75%}), maximum expiratory flow₇₅ (MEF₇₅), maximum expiratory flow₅₀ (MEF₅₀), maximum expiratory flow₂₅ (MEF₂₅) with a portable digital spirometer with a portable digital spirometer. In addition, exercise tolerance will be assessed by change in 6 minute walk distance (6MWD) in 6 minute walk test (6MWT). Changes in peripheral capillary oxygen saturation (SpO₂) by Pulse Oximeter and degree of dyspnea and fatigue by Modified Borg Scale (MBS) will also be measured both before and after 6MWT, to evaluate their changes in both the groups. All these variables will be again measured on their follow-up in 13 weeks and 26 weeks with standard pharmacological treatment of ACO with D₃ intervention (B group) and also without D₃ intervention (A group). The data will be statistically analyzed by Graphpad prism (Version 7) using independent sample 't' test (between two groups), paired Student's 't' test (between paired groups before and after intervention). Group comparisons will be done using one way ANOVA. In the interpretation of results, ≤0.05 level of probability (p) will be accepted as significant.

Expected outcome of the study:

- Impaired lung functions and exercise tolerance in vitamin D₃ deficient ACO patients will be detected and the good impact of vitamin D₃ supplementation for six months on restoration of the lung function status and exercise tolerance in ACO patients will be proved.

Key words: Asthma COPD Overlap, Vitamin D₃, FVC, FEV₁, FEV₁/FVC%, FEF_{25-75%}, PEF_R, MEF_{75%}, MEF_{50%}, MEF_{25%}, SpO₂, 6 Minute Walk Distance, Modified BORG scale.

Introduction

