Is there any improvement in lung function status and exercise tolerance in vitamin D₃ deficient ACO patients after having vitamin D₃ supplementation?

Hypothesis

Null: Vitamin D₃ supplementation does not improve lung functions and exercise tolerance in vitamin D deficient ACO patient.

Alternate: Vitamin D₃ supplementation improves lung functions and exercise tolerance in vitamin D deficient ACO patient.

Objectives:

General objectives:

To evaluate the effects of vitamin D₃ supplementation on lung function status and exercise tolerance in D₃ deficient, stable patients with ACO.

Specific objectives

- To measure the FVC, FEV₁, FEV₆, FEV₁/FVC%, PEFR and FEF_{25-75%} of vitamin D₃ deficient, stable patients with ACO, in order to assess their lung function status at baseline.
- To measure the 6MWD of all the patients, in order to assess their functional exercise capacity at baseline.
- To measure the SpO₂ at rest of all the patients, in order to assess the basal oxygenation status at baseline.
- To measure the level of dyspnea and fatigue at rest of all the patients in order to assess the basal breathlessness level at baseline.
- To measure the both the SpO₂ and level of dyspnea and fatigue again after 6MWT, for the assessment of their exercise tolerance at baseline.
- To measure the all these variables in study group at 13th weeks and at 26th weeks of their follow up.
- To measure the all these variables in control group at 13th weeks and at 26th weeks of their follow up.
- To compare all these variables in study group at baseline and endline.
- To compare all these variables in control group at baseline and endline
- To compare all these variables in both group at baseline and endline.

Methods

Type of study	: Double blinded placebo controlled trial
Place of study	: Department of Physiology, Bangabandhu Sheikh Mujib Medical University (BSMMU), Shahbagh, Dhaka
Period of study	: March 2018 to February 2019
Study population	: Stable patients of ACO with vitamin D ₃ deficiency
Sample size	: 60
Sampling	: Consecutive sampling
Grouping	:
Group A (Control)	: 30 (thirty) D ₃ deficient ACO patients with placebo administration
Group B (Study)	: 30 (thirty) D ₃ deficient ACO patients with vitamin D ₃ administration

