If the patient with D₃ deficiency [Serum 25(OH)D <30 ng/ml] and not with renal insufficiency (Serum creatinine >1.3 mg/dl), then the Fasting blood sugar, serum HbA_{1c}, serum parathormone (PTH), serum calcium (Ca²⁺), serum phosphate (PO₄³⁻), serum alkaline phosphatase (ALP), serum SGPT, serum cholesterol, serum High Density Lipoprotein (HDL), serum low density lipoprotein (LDL), serum triglyceride (TG), will be assessed from the preserved blood.

After that their height and weight will be measured and the spirometric lung function test will be done by using a portable spirometer (PONY FX, cosmed, Italy]. After getting all the biochemical and spirometric reports the final selection will be done, according to the inclusion and exclusion criteria. All the eligible patients will be randomly assigned to either 'Control' or 'Study' groups and will be thoroughly informed about the objectives and detailed study procedure, once again.

Subsequently a standard therapeutic treatment (according to GOLD guideline) will be prescribed to all the selected stable ACO patients of both groups. Proper education will be given about drug, method of taking medication and medication plan.

Along with the standard pharmacological treatment of ACO, the patients of the 'Study group' will be prescribed for 80,000 IU/ week of oral vitamin D₃, for consecutive 13 weeks. Subsequently, all the patients will be cordially requested to again visit the Department of physiology, BSMMU, on 13th week of their follow up to reexamine all the study

variables along with serum 25(OH)D and Ca^{2+} (to check the toxicity). These data will be recorded as values of '13th week' (B13).

Then according to serum level of 25(OH)D and Ca^{2+} (American Vitamin D council 2017), 40,000 IU / 1 to 6 week oral vitamin D₃ will be prescribed, for further 13 weeks. At 26th week of follow up, they will be requested again to visit the Department of Physiology, BSMMU, to reexamine all the study variables, and the data will be recorded as values of '26th week' (B26).

Similarly, all the patients of 'control group' will be prescribed for placebo (along with standard pharmacological treatment of ACO, prescribed by pulmonologist) for consecutive 26 weeks and their respective data will be recorded as A13 and A26.

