The 6MWT will be performed at indoors, along a long, flat, straight, enclosed corridor with a hard surface that was seldom traveled. The walking course will be 30 meter in length which was marked every 3 meter. The turnaround points will be marked with a cone. A starting line, which marked the beginning and end of each 6 meter lap, will be marked on the floor using brightly colored tape.

The subject will be asked to walk at his own maximal pace along the corridor from the end, covering as much ground as he can, during the allotted time, without running. He will be also advised to take rest if he

was too exhausted to continue the test. Standard phrases at regular intervals (every 60 seconds) will be used, like: “you are doing well,” “keep up the good work”. At the same time he will be also informed about the past time and how much left before the test completed.

If any of the subjects develop chest pain, intolerable dyspnea, leg cramps, staggering, diaphoresis or pale appearance the test will be immediately stopped and the subject will be dropped. Again, when any subject will complete the total test procedure (according to the exact protocol), he will be congratulated for good effort.

Vitamin and placebo administration

	Vitamin D₃	Placebo
Collection	Beximco Pharmaceuticals Limited, Bangladesh	Beximco Pharmaceuticals Limited, Bangladesh
Dose	80,000 IU/wk	80,000 IU/wk
Route	Oral	Oral
Ingredient	
• Cholecalciferol (40,000IU)• Microcrystalline Cellulose (58.1 gm)• Butylated Hydroxy Toluene (0.2mg)• Magnesium Stearate (3mg)• Gelatin Capsule Shell (1mg)	
• Microcrystalline Cellulose (303.8gm)• Butylated Hydroxy Toluene (0.2mg)• Magnesium Stearate (3mg)• Gelatin Capsule Shell (1mg)

STATISTICAL ANALYSIS

TITLE

**Effects of vitamin D₃ supplementation on lung functions and
exercise tolerance in D₃ deficient Asthma COPD Overlap
(ACO) patients**

Date: 06/09/2018

The results will be expressed as mean with standard error (mean \pm SE). The data will be statistically analyzed by Graphpad prism (Version 7) using independent sample 't' test (between two groups), paired Student's 't' test (between paired groups before and after intervention). Group comparisons will be done using one way ANOVA. Correlations between variables will be tested with Pearson correlation coefficient.

In the interpretation of results, ≤ 0.05 level of probability (p) will be accepted as significant.

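### The only between-arm test named is an independent t-test with no baseline covariate, so the treatment comparison is less precise than the day-0 data allow

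*Combined protocol and SAP*

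**What the plan says.** The Statistical Analysis section, which repeats most of the Project Summary's wording, lists four methods:

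- between arms, an independent-sample t-test: "using independent sample 't' test (between two groups");
- within arms, a paired t-test: "paired Student's 't' test (between paired groups before and after intervention");
- "Group comparisons will be done using one way ANOVA";
- Pearson correlation.

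It names no covariate, ANCOVA, mixed model or between-arm test of change.

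The between-arm item under Specific objectives is "To compare all these variables in both group at baseline and endline", a comparison of the arms at each of two times. One sentence in the Project Summary points another way: "exercise tolerance will be assessed by change in 6 minute walk distance (6MWD"). The Statistical Analysis section does not take it up.

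Baseline outcomes are collected in everyone. For the walk test, for example, the objective is "To measure the 6MWD of all the patients, in order to assess their functional exercise capacity at baseline". Spirometry, SpO2 and the Borg scores are also recorded at day 0.

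On allocation, Study procedure says "All the eligible patients will be randomly assigned to either 'Control' or 'Study' groups", with no stratification described. The Project Summary adds "All the participants will be matched in terms of age, duration of ACO, duration of smoking, body mass index (BMI") and continues with further anthropometric, social and biochemical variables. No spirometric, walk-test, SpO2 or Borg variable is on that list.

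**The concern.** The day-0 value of an outcome usually predicts its week-26 value. A between-arm test that leaves it out keeps the predictable part of the patient-to-patient variation in the error term. A test of change uses the baseline, but with a fixed coefficient of 1 where ANCOVA estimates the coefficient.

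Two things are at stake. The treatment effect is estimated with a wider interval than the collected data permit. And if the arms happen to differ at day 0 on an outcome, part of that difference reappears at week 26, where an unadjusted endline test cannot separate it from treatment. Testing the baseline difference separately does not remove it, and the paired tests within each arm do not compare the arms.

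**Working it through.** **Inputs.** From Sample size calculation: means 364.1 and 357.3 (difference 6.8), SDs 7.21 and 12.25, Zα = 1.96, Zβ = 0.84. Arm size is 35 from that calculation and 30 in the Methods table; both are shown. The correlation r between day-0 and week-26 values is not in the documents, so r = 0.3 to 0.8 is assumed. Equal SDs at the two times are also assumed.

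**The plan's own figure.** (1.96 + 0.84)² × (7.21² + 12.25²) / 6.8² = 7.84 × 202.0466 / 46.24 = 34.26, rounded up to 35 per group. This reproduces. It uses unadjusted means and SDs, so r plays no part in it.

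**Planning scale.** SD = √(202.0466 / 2) = 10.05. Standardised difference = 6.8 / 10.05 = 0.68.

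**Variance of the arm difference, relative to an endline-only t-test**

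- Endline t-test: 1
- t-test on change: 2(1 − r)
- ANCOVA: 1 − r² = (1 − r)(1 + r)

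ANCOVA is below 1 for any non-zero r. Its ratio to the change-score test is (1 + r)/2, which is below 1 for any r below 1. So ANCOVA is the more precise whichever way the t-test is read. These are large-sample ratios. They ignore the cost of estimating one slope, which is small at this sample size.

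| r | Change | ANCOVA | SE reduction, ANCOVA against endline |
|---|---|---|---|
| 0.3 | 1.40 | 0.91 | 5% |
| 0.5 | 1.00 | 0.75 | 13% |
| 0.7 | 0.60 | 0.51 | 29% |
| 0.8 | 0.40 | 0.36 | 40% |

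**Illustrative power.** Noncentral t, two-sided 5%, difference 6.8. The SD is 10.05 for the endline test, 10.05 × √(2(1 − r)) for change and 10.05 × √(1 − r²) for ANCOVA.

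| | 35 per arm | 30 per arm |
|---|---|---|
| Endline t-test | 79.7% | 73.1% |
| ANCOVA, r = 0.3 | 83.3% | 77.0% |
| ANCOVA, r = 0.5 | 89.6% | 84.5% |
| ANCOVA, r = 0.7 | 97.4% | 95.0% |
| ANCOVA, r = 0.8 | 99.6% | 99.0% |

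A t-test on change at 35 per arm gives 65.5% at r = 0.3, 79.7% at r = 0.5 and 95.0% at r = 0.7. Below r = 0.5 it does worse than the endline test.

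**Carry-over of a chance imbalance (endline t-test).** The SE of a day-0 difference at 35 per arm is √(2/35) = 0.24 SD, or 2.40 units if the day-0 SD is also 10.05. An imbalance of one SE shifts the expected endline difference by r × 2.40:

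- r = 0.3: 0.72, or 11% of 6.8
- r = 0.5: 1.20, or 18%
- r = 0.7: 1.68, or 25%
- r = 0.8: 1.92, or 28%

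Conditional on an imbalance of k SEs, the test statistic under no effect has mean r × k and SD √(1 − r²). At k = 1.96 the type I error of the nominal 5% test is about 13% (r = 0.5) to 21% (r = 0.7). At k = 1 it is slightly below 5%. Averaged over all imbalances it is about 5%.

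**The case against.** **The plan may not ignore baseline.** A reader might infer that the t-test is run on raw endline values for every outcome. The documents do not settle this. The objectives suggest it, but the Project Summary refers to change in 6MWD, and that phrase is itself unclear. This stands as a limit on what can be claimed. It does not rescue the plan, because a change-score test is also less precise than ANCOVA for r below 1.

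**The test is valid.** A reader might infer that the planned comparison is biased or has an inflated error rate. It does not: allocation is random, and the t-test's standard error already includes chance imbalance. The distortion shown above is conditional on an imbalance that has been observed. This stands in full.

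**The size is not known.** The documents give no correlation and no evidence that patients differ by large and stable amounts. The only SDs, 7.21 and 12.25, are about 2% and 3% of their means. Correlation may be low for coarse scores such as Borg, and standard therapy is prescribed after the baseline tests, which could weaken it further. At r = 0.3 the gain is modest. This stands, and is why the range starts there.

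**The power figures belong to no named outcome.** Sample size calculation does not say what was measured, and the control mean is the higher one. A reader should not take the 83% to 99% figures as this trial's power. The variance ratios do not depend on those inputs.

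**Matching and narrow eligibility may help.** They may reduce some variation, but no outcome variable is on the matching list and the matching method is not described. They do not replace adjustment for the baseline outcome.

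**Conclusion.** The point holds as an efficiency weakness in a valid test. No baseline-adjusted treatment contrast is specified although the data for one are collected. Whether the t-test is meant for endline values or for changes, ANCOVA is at least as precise, and strictly more so for r between 0 and 1.

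The direction is certain and the size is not. Against an endline t-test, the variance falls by 9% at r = 0.3 and by 64% at r = 0.8, under assumed correlations that may differ between spirometry, walk distance, SpO2 and Borg scores. The power figures are illustrations on a difference whose outcome is not stated. The plan should be changed on this point, but the planned analysis would not be invalid without the change.

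**What to change.** For each outcome, pre-specify the between-arm analysis as a linear model of the week-26 value on arm and the day-0 value of the same variable. State that the adjusted arm difference, with its 95% confidence interval, is the treatment effect. Use the same model at week 13 if that visit is reported. For the bounded outcomes (Borg scores and SpO2), check the model fit or add a rank-based sensitivity analysis. Dropping the baseline significance test is optional.

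The cost is a few lines in the Statistical Analysis section and a regression in place of a t-test, in another package if the named one does not fit covariate models. No extra patients, visits or measurements are needed. Separately, the 35 and 30 per arm should be reconciled.

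### Between-arm t test, within-arm paired t tests and an undefined one-way ANOVA are all read at p ≤ 0.05; none is named as the efficacy test, and the between-arm test is not adjusted for day 0

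*Combined protocol and SAP*

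**What the plan says.** The Statistical Analysis section names four techniques: an independent-sample t test for the two groups, a paired t test within groups, a one-way ANOVA and Pearson correlations. The purpose of the paired test and of the ANOVA is given only as "between paired groups before and after intervention). Group comparisons will be done using one way ANOVA", and the Project Summary repeats the same three comparison tests. One threshold covers everything: a ≤ 0.05 "level of probability (p) will be accepted as significant".

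The Specific objectives list three comparisons side by side, with no ranking:

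- Within the study arm: "To compare all these variables in study group at baseline and endline".
- Within the control arm: the identical before-and-after objective, worded the same way.
- Between the arms: "To compare all these variables in both group at baseline and endline".

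The null hypothesis names no comparator: "Null: Vitamin D₃ supplementation does not improve lung functions and exercise tolerance in vitamin D deficient ACO patient".

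The Project Summary says "exercise tolerance will be assessed by change in 6 minute walk distance (6MWD", but the analysis section does not tie a change score, or a week-26 value, to any test. The Methods define six group-by-visit cells (A₀–A₂ and B₀–B₂). The sample size calculation uses a formula for two independent means and arrives at 35 per group.

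**The concern.** The three tests answer different questions, and they can disagree on the same data.

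- **Paired test in the study arm.** It asks whether patients changed between day 0 and week 26. Under Study procedure, both arms are prescribed standard treatment after randomisation, with education on medication and advice on sun exposure. Appendix III includes inhaled corticosteroid and smoking-cessation advice, while the Exclusion criteria rule out glucocorticoids in the preceding month. If that exclusion covers inhaled drugs, both arms would start them during the trial; the two passages need reconciling. The four-week stability requirement in the Project Summary points towards little change. The size of any change common to both arms is therefore unknown.
- **One-way ANOVA.** With two arms at one visit it duplicates the t test. Across the six cells treated as independent it is invalid, because the same patients appear three times. As a repeated-measures ANOVA within an arm it can be valid for visits, but it does not compare treatments.
- **Between-arm t test.** This is valid and is the only listed test that directly addresses the treatment question. As written it has no day-0 covariate.

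At stake is whether the basis for an efficacy claim is fixed in advance. As the text stands, a report resting on the study-arm paired test would be consistent with the plan. Separately, the day-0 measurements are collected but not used to sharpen the between-arm comparison.

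**Working it through.** **Inputs from the protocol (Sample size calculation, Methods).** Means 364.1 and 357.3, a difference of 6.8; SD 7.21 (control) and 12.25 (study); Z values 1.96 and 0.84; 35 per group in the calculation, 30 per group in Methods.

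**Assumptions, not given in the documents.** Day-0 to week-26 correlation r; a change common to both arms of 0, 2 or 4 units at weeks 13 and 26; equal correlation between visits; normal data; SDs larger than those stated. All rejections are two-sided at 0.05.

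**1. The plan's own figure.** n = (1.96 + 0.84)² × (7.21² + 12.25²) / 6.8² = 7.84 × 202.0466 / 46.24 = 34.26, rounded up to 35. It reproduces, and it is the formula for an unadjusted between-arm comparison. The pooled SD is √(202.0466/2) = 10.05.

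**2. Study-arm paired test with no vitamin D effect.** The SD of change is SD × √(2(1 − r)). For SD 12.25, r = 0.5 and n = 35, that is 12.25, with standard error 12.25/√35 = 2.07. A common change of 4 gives a non-centrality of 4/2.07 = 1.93 and a rejection probability of 46.7% (34 df). Over r = 0.5 to 0.8:

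| SD | Common change 2 | Common change 4 |
|---|---|---|
| 12.25 (stated) | 16–32% | 47–84% |
| 10.05 (pooled) | 21–44% | 63–95% |
| 24.5 (stated SD doubled) | 8–12% | 16–32% |
| 50 | about 6% | 8–11% |

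**3. Other readings of the plan with no vitamin D effect** (simulation, 35 per arm, r = 0.5 to 0.8):

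| Reading | No change | Change 2 | Change 4 |
|---|---|---|---|
| Between-arm t test or ANCOVA | about 5% | about 5% | about 5% |
| Study arm significant, control not; stated SDs | about 5% | 9–10% | 0.1–5% |
| Same, pooled SD | about 5% | 16–24% | 5–23% |
| Repeated-measures ANOVA in study arm; stated SDs | 5% | 15–32% | 48–88% |
| Six cells as independent | 4–5% | 8–9% | 38–46% |

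Accepting either the study-arm paired test or the between-arm t test gives 9–10% with no common change. As a rough check, two independent tests would give 1 − 0.95² = 9.75%.

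**4. Precision of the between-arm test for a true difference of 6.8.** The week-26 t test has standard error 10.05 × √(2/35) = 2.40 and non-centrality 6.8/2.40 = 2.83, giving power of 79.7%. ANCOVA reduces the residual variance by the factor 1 − r², equivalent to 35/(1 − r²) patients per arm: 38.5 at r = 0.3, 46.7 at r = 0.5 and 68.6 at r = 0.7.

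| Power | r = 0 | 0.3 | 0.5 | 0.7 | 0.8 |
|---|---|---|---|---|---|
| Week-26 t test, 35 per arm | 80% | 80% | 80% | 80% | 80% |
| Change-score t test, 35 per arm | 50% | 66% | 80% | 95% | 99% |
| ANCOVA, 35 per arm | 79% | 83% | 89% | 97% | >99% |
| Week-26 t test, 30 per arm | 73% | 73% | 73% | 73% | 73% |
| ANCOVA, 30 per arm | 72% | 76% | 84% | 95% | 99% |

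**The case against.** The best reply is that the intended comparison can be inferred. The trial is randomised and placebo controlled, it is sized with a two-mean formula, and one objective compares the two groups. Listing paired tests is not a declaration that they will support an efficacy claim. That is fair: the defect is an unstated hierarchy, and the plan does not commit itself to the wrong test. It does not remove the point, because the research question is framed as improvement after supplementation, the null hypothesis has no comparator, and the within-arm objectives have equal standing.

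The false-positive figures also depend on assumptions. The documents give no common change of 2 or 4 units, and at SD 50 the paired-test rate is only 6–11%. With the stated SDs and a change of 4, the pattern of study arm significant and control arm not is at or below its 5% floor. The 9–10% figure needs no common change, but it supposes an either-test rule that the plan does not state. So the sizes are illustrative. That a within-arm test does not isolate a vitamin D effect does not depend on them.

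On adjustment, the unadjusted t test is valid and agrees with the sample size formula. If the sponsor means to analyse change, day 0 is already used, and at r = 0.7 or above the gain from ANCOVA almost disappears (95% against 97%). At r = 0.5 it remains (80% against 89%). The gain also depends on the SD: at an assumed SD of 50, power for 6.8 is about 9% unadjusted, 10% with ANCOVA at r = 0.5 and 15% at r = 0.8. This part is an improvement in precision; no error is being corrected.

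**Conclusion.** The concern holds, on the protocol and SAP text available for review (some pages had been removed). That text does not say which of three tests would reject the null hypothesis, leaves the ANOVA undefined, and specifies a between-arm test without a day-0 covariate. The between-arm t test keeps its 5% error rate in every setting examined. The study-arm paired test does so only if nothing common to both arms changes; its excess ranges from about one percentage point to most trials, depending on an unknown common change, SD and correlation. The missing adjustment is lost precision, worth roughly 9 to 10 points of power at r = 0.5 with the stated SDs if week-26 values are compared, nothing at r = 0, and little if the SD is much larger. It should be fixed. The valid test is already listed, so the remedy is to make it decisive.

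**What to change.** State in the Statistical Analysis section that:

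1. Efficacy is judged only on the between-arm difference at week 26, estimated by ANCOVA with group and the day-0 value of the outcome as terms, and reported with a 95% confidence interval.
2. This analysis applies first to the outcome the sponsor designates as primary, with other outcomes supportive. The absence of a named primary outcome is a separate point.
3. Paired day-0 to week-26 changes are shown for both arms as description, with no efficacy claim attached.
4. The one-way ANOVA is dropped, or its factor and data structure are defined and it is kept descriptive.

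The cost is SAP wording, slightly more analysis work and possibly a regression package alongside the named software. No new data are needed, because day-0 values are already recorded.

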For the assessment of all the variables of all the patients on day 0, at 13th week and as well as at 26th week, they will be designated as A₀, A₁ and A₂ (control) and B₀, B₁ and B₂ (study). In addition, for the mean of SpO₂, level of dyspnea and level of fatigue at resting condition (before 6MWT), all the groups will be further designated as A_{0before}, A_{1before}, A_{2before}, B_{0before}, B_{1before} and B_{2before} respectively. Similarly after 6MWT all these six subgroups will be again designated as A_{0after}, A_{1after}, A_{2after} and B_{0after}, B_{1after}, B_{2after}, for measurement of these three variables.

Sample size calculation

Using the following statistical formula

$$n = [(Z\alpha + Z\beta)^2 \times (\sigma_1^2 + \sigma_2^2)] / (\mu_1 - \mu_2)^2$$

(Kirkwood and Sterne 2003)

$$\text{Mean of control, } \mu_1 = 364.1$$

$$\text{Mean of study group, } \mu_2 = 357.3$$

$$\text{SD of control, } \sigma_1 = 7.21$$

$$\text{SD of study group, } \sigma_2 = 12.25$$

(Hassan 2018)

$$\text{Type I Error, } Z\alpha = 1.96$$

$$\text{Type II Error, } Z\beta = 0.84$$

(Kirkwood and Sterne 2003)

Therefore,

$$\begin{aligned} n &= [(Z\alpha + Z\beta)^2 \times (\sigma_1^2 + \sigma_2^2)] / (\mu_1 - \mu_2)^2 \\ &= [(1.96 + 0.84)^2 \times (7.21^2 + 12.25^2)] / (364.1 - 357.3)^2 \\ &= [7.84 \times (51.9841 + 150.0625)] / (6.8)^2 \\ &= 1584.04534 / 46.24 \\ &= 34.2570359 \\ &= \text{approximately 35 for each group.} \end{aligned}$$

Subject selection:

Inclusion criteria

- Pulmonologist diagnosed stable patient of ACO
(GINA and GOLD 2015)
- Duration of ACO: > 4 year
- Vitamin D₃ deficient : Serum 25(OH)D <30 ng/ml
(Vitamin D Council 2017)
- Age: 40 -70 years
- Sex: Male
- Socioeconomic status: middle class
- Smoker
- Anthropometric status:
 - BMI=18.6-24.9 kg/m²
(WHO 2006)
 - mid upper arm circumference>25.1 cm
(Sultana et al. 2015)
 - waist-hip ratio<0.89
(Sultana et al. 2015)
- Serum parathormone: 10-65 pg/ml
- Serum Ca²⁺: 8.5-10.5 mg/dl
- Serum PO₄³⁻: 2.3-4.7 mg/dl
- Serum alkaline phosphatase: 30-120 U/L
- SGPT: <50 U/L
- Serum creatinine: 0.7-1.3 mg/dl
- FBS: 3.5-6.1 mmol/L
- Serum HbA1c: 4.5-6.3 %

- Serum cholesterol: <200 mg/dl
- Serum HDL: >40 mg/dl,
- Serum LDL: <130 mg/dl
- Serum TG: <150 mg/dl

Exclusion criteria

With history of:

[figure not shown]
- any other pulmonary diseases, as,
 - ✓ chronic obstructive pulmonary disease
 - ✓ bronchial asthma
 - ✓ respiratory tract infection
 - ✓ bronchiectasis
 - ✓ pleural effusion
 - ✓ tuberculosis

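### One-way ANOVA is listed without a factor: on the two arms it only repeats the t-test, and across visits it treats the same patients as independent groups and cannot isolate vitamin D

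*Combined protocol and SAP*

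**What the plan says.** The STATISTICAL ANALYSIS section, and the Project Summary in the same terms, list three tests for comparing means:

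- an independent t-test, "using independent sample 't' test (between two groups";
- a paired t-test, "between paired groups before and after intervention";
- a third tool: "Group comparisons will be done using one way ANOVA".

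For the third, the plan names no factor, visit, repeated-measures term, arm-by-time interaction or follow-up contrast.

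On design, the Study procedure section says "All the eligible patients will be randomly assigned to either 'Control' or 'Study' groups", so there are two randomised groups. The Methods section then labels the data by arm and visit, "For the assessment of all the variables of all the patients on day 0, at 13th week and as well as at 26th week", as A0, A1, A2 for control and B0, B1, B2 for study. It treats these as groups in their own right: "Similarly after 6MWT all these six subgroups will be again designated as" introduces a further set of labels for the measurements after the walk test. The last specific objective is "To compare all these variables in both group at baseline and endline".

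**The concern.** With two arms and an independent t-test already listed, an ANOVA adds something only if it is run on three or more groups. The only such sets in the document are the visit labels, and A0, A1 and A2 are one set of patients measured three times, as are B0, B1 and B2.

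Ordinary one-way ANOVA assumes independent observations. Applied to these labels it has two faults:

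- **Error term.** Stable differences between patients are counted as error, so the yardstick for change over time is too large.
- **Hypothesis.** Across all six cells the null is that all six means are equal. It is false whenever both arms change together, whatever vitamin D does.

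A shared change is plausible here. After selection, patients in both arms are prescribed standard treatment with education on taking it. Both are also advised on daily sunlight exposure and, in Appendix III, on stopping smoking. A significant six-cell F could come wholly from these and be mistaken for a vitamin D effect.

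**Working it through.** **Inputs from the document.** Two arms; three visits; significance at p ≤ 0.05; Zα = 1.96 and Zβ = 0.84; SDs 7.21 and 12.25; difference 364.1 − 357.3 = 6.8. The calculation gives 35 per group, while the Methods table gives 30.

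**The plan's own figure.** n = (1.96 + 0.84)² × (7.21² + 12.25²) / 6.8² = 1584.05 / 46.24 = 34.26, so 35 per group. It reproduces. It is a two-group calculation and does not depend on the ANOVA.

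**Assumptions.** The document gives no between-visit correlation r and no expected course over time. I assume unit SD, equal correlation between visits (r = 0.6 or 0.8), a change of 0, 0.25 and 0.5 SD at the three visits, and 20,000 simulated trials per setting.

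**Reading 1: two arms at one visit.** One-way ANOVA gives F = t². In a test data set with 35 per arm, t = −1.4245, F = 2.0291 and p = 0.1589 both ways. It is valid and redundant.

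**Reading 2: three visits within one arm.** The SE of a difference between two visit means should be √(2(1 − r)/n). One-way ANOVA uses √(2/n), which is too large by 1/√(1 − r).

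| n = 35 | r = 0.6 | r = 0.8 |
|---|---|---|
| SE used, √(2/35) | 0.239 | 0.239 |
| Correct SE | 0.151 | 0.107 |
| Overstatement | 1.6 times | 2.2 times |
| Rejection with no change (nominal 5%) | 0.1% | 0.0% |
| Power, one-way ANOVA | 33% | 26% |
| Power, repeated-measures ANOVA | 83% | 99% |
| Power, planned paired t-test, day 0 to week 26 | 89% | 99.5% |

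The last row follows from the noncentrality 0.5/√(2(1 − r)/35) = 3.31 and 4.68.

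**Reading 3: all six cells.** The F-test responds to the spread of the six means around their average.

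- Same change in both arms, no vitamin D effect: means 0, 0.25, 0.5, 0, 0.25, 0.5; average 0.25; sum of squares 4 × 0.25² = 0.250.
- Change in the study arm only: means 0, 0, 0, 0, 0.25, 0.5; average 0.125; sum of squares 5 × 0.125² + 0.375² = 0.219.

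So the shared change gives the larger signal.

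| n = 35, six-cell F significant | r = 0.6 | r = 0.8 |
|---|---|---|
| No change in either arm | 4.0% | 4.9% |
| Same change in both arms, no vitamin D effect | 56% | 52% |
| Change in the study arm only | 42% | 37% |

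Repeat runs differ by about one percentage point.

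**At 30 per group.** The pattern is the same. Within-arm power is 26% and 17%, against 77% and 97% for repeated-measures ANOVA. The six-cell F is significant in 46% and 39% of trials with a shared change, and in 35% and 31% with a study-arm change only.

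**The case against.** The strongest reply is that the plan never says the ANOVA will be run across visits. The grouping entry in Methods defines only groups A and B, and on those the ANOVA is valid and does compare vitamin D with placebo. This stands in part: the use across visits is inferred. But on the two-arm reading the sentence adds nothing, and a repeated-measures form, if meant, is not written down. Every reading calls for a change of text.

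Second, the stated objectives (each arm at baseline and endline, and the two arms against each other) are all covered by the two t-tests. This stands. A reader might infer that real change over time will be missed. The document does not support that, because the planned paired t-test uses the correct within-patient error and detects the assumed change as well as repeated-measures ANOVA does.

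Third, a reader might infer that false positives are inflated, or that the trial has no valid comparison of the arms. Neither holds. With no change anywhere, the within-arm test rejects far too rarely and the six-cell test near the nominal 5%. The independent t-test remains a valid comparison of the arms at one visit.

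Fourth, the 56% and 52% are correct rejections of a null that is false. They become a wrong claim only if the F is read as a treatment effect, and nothing says it will be. That is fair, but nothing in the plan gives the t-test precedence over the ANOVA at p ≤ 0.05 either.

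**Conclusion.** The point holds as a should-fix. The ANOVA's factor is undefined. On the two arms the test is redundant. On the only larger sets of groups in the document it is unsuitable: very conservative within an arm, and across six cells unable to separate change over time from treatment. A significant six-cell F would therefore not be evidence for vitamin D.

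The fault of hypothesis matters more than the error term, because the paired t-test already covers change within an arm. The sizes rest on assumed correlations, an assumed course of change and 35 per arm. The F = t² identity and the mismatch between the six-cell null and the trial's question do not depend on those assumptions.

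**What to change.** Delete the one-way ANOVA sentence from the STATISTICAL ANALYSIS section and the Project Summary. In its place:

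1. Take the vitamin D versus placebo contrast at weeks 13 and 26 from a baseline-adjusted model. This can be an ANCOVA at each visit with the day-0 value as covariate, or one mixed model per outcome with arm, visit, arm-by-visit and day-0 value, and patient as the repeated unit.
2. Describe change within an arm only with the paired t-test or a repeated-measures analysis, and state that it is not read as a treatment effect.

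Baseline adjustment also gains power. For a 0.5 SD between-arm effect at week 26 with 35 per arm, the unadjusted t-test has noncentrality 0.5/√(2/35) = 2.09 and 54% power. ANCOVA has 0.5/√(2(1 − r²)/35) = 2.61 at r = 0.6 and 3.49 at r = 0.8, or 73% and 93% power.

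The cost is rewording the plan, and possibly software other than the named GraphPad Prism 7. No new data, visits or patients are needed.
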